3.3.6. Presentations by Study Visit

The daily electronic diary entries reported during the Treatment Period will be classified into 4 weeks – Week 1 (Day 1-7); Week 2 (Day 8-14); Week 3 (Day 15-21); Week 4 (Day 22-28); Week 5 (Day 29-35); Week 6 (Day 36-49).

Non-diary data, such as vital signs and clinical laboratory assessments, will be displayed and analyzed according to the nominal visit date on the eCRF unless the visit is an unscheduled visit. Unscheduled visit values will be used if the unscheduled visit falls in a visit window and the scheduled visit from the same visit window has a missing value. Visit windows will be calculated as follows for vital signs, urine pregnancy test, and physical examination:

Nominal Visit	Minimum Study Day	Maximum Study Day
Screening Week -4	-28	-1
Week 1	1	14
Week 4	15	35
Post-Treatment Week 6	36	49

Visit windows for serum chemistry, hematology, and urinalysis will be calculated as follows:

Nominal Visit	Minimum Study Day	Maximum Study Day
Screening Week -4	-28	-1
Week 1	1	14
Week 4	15	45

If assessments are collected multiple times within a given Study Visit window, the result closest to the scheduled visit date will be used for summary presentations. If two measurements have the same distance to the expected date, the latest result will be used. If a subject has multiple non-missing scheduled values on the same date, the latest result in terms of time will be used. All assessments will be presented in the listings.

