6.4.1 Packaging

Each investigational drug kit will be supplied in blister packaging. At the randomization visit (Day 1), eligible patients enrolled in treatment group A (6 to 11 years old) will receive one drug kit for the entire 4 weeks of dosing (Weeks 1, 2, 3, and 4) 28 days plus 4 additional tablets to allow for a +3-day window. Patients in treatment group B (12 to < 18 years old) will receive two drug kits and will be instructed to take one tablet from each drug kit (2 tablets daily) for the entire 4 weeks of dosing (56 tablets) plus 8 additional tablets to allow for a +3-day window. Patients will be instructed to bring their kits to the EOT or EW study visit for determination of compliance and reconciliation of supplies.

Each investigational study drug kit will contain 32 tablets. Individually blister-packaged tablets will be provided in four connected strips (of 8 tablets) as a 4-panel key-pack that folds into a carton. The two bottom panels fold up into the two top panels, nesting blister cavities. Instructions for releasing a tablet from the blister dome are printed on the outside of the carton.

Clinical sites will save all empty packaging or packaging containing unused tablets for final disposition instructions from the sponsor.

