Treatment Period: Subjects 6 to 11 years of age (Group A) who meet all entry criteria will be randomly assigned to 1 of 3 dose groups (2 active treatment, 1 matching placebo) in a 1:1:1 ratio stratified by gender; subjects 12 to < 18 years of age (Group B) will be randomly assigned to 1 of 4 dose groups (3 active treatment, 1 matching placebo) in a 1:1:1:1 ratio stratified by gender on Day 1 of the Treatment Period. Randomization will be stratified by gender to ensure gender balance across treatment groups within each age group. Subjects will take their daily oral dose of the study drug once daily for 4 weeks and continue to complete their daily electronic diaries recording BMs, rescue medication use for constipation, and abdominal pain and other symptoms. At Weeks 1 and 4 of the Treatment Period, subjects will return to the clinic to undergo safety and efficacy assessments.

Post-treatment Follow-up Period: For 2 weeks after the last dose of study drug, subjects will continue to complete their daily electronic diaries. Subjects will then return to the clinic for a final Follow-up visit at the end of Week 6.

The planned duration of participation in this study will be approximately 10 weeks from signing of informed consent/assent through post-treatment.

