3.3.7. Definitions and Terminology

Age

The age of a subject is defined as the number of whole years between the subject's birth date and the date of screening. If a subject is anticipated to turn 12 between screening and randomization, he/she will be randomized into the adolescent group but will use the Wong Baker and the mBSFS. A subject who turns 12 during the treatment period or post-treatment follow-up period will remain in 6 to 11 years age group and will use the Wong Baker and the mBSFS. The questionnaires will be provided based on the age at Screening.

All subjects in 6 to 11 years old age group are expected to get the parental oversight on eDiary records. All subjects in 12 to <18 years old age group can complete eDiary by themselves but should be discussed with parent.

Baseline Value

For purposes of safety analysis, the baseline value is defined as the last non-missing value obtained prior to the randomization.

For purposes of efficacy analysis, the baseline values will be derived from data collected in the 2-week electronic diary assessment at the end of the Screening Period (baseline). The last 14 days of diary entries prior to Day 1 will be the default standard for derivation of these values.

The baseline BM (SBM, CSBM) weekly rate will be the weekly average number of BMs (SBMs, CSBMs) recorded during the 2-week baseline assessment period; similarly, for frequency of abdominal pain and abdominal discomfort, frequency of fecal incontinence, frequency of defecation pain, and frequency of large diameter stools. Baseline stool consistency, severity of abdominal pain, abdominal discomfort, and severity of defecation pain will be calculated as follows: for each week of the baseline assessment, the weekly average is the sum of the non-missing scores recorded during the week divided by the total number of non-missing scores recorded during that week; the baseline is then equal to the average of the 2 weekly average scores defined as sum of the 2 weekly average scores divided by 2.

Day 1 (Baseline)

Day 1 is the earliest day that study drug is initiated.

Study Day

Study Day is defined relative to Baseline (Day 1). Thus, the study day of an event is calculated as:

Study Day = Event Start Date – Baseline Date + 1, for dates on or after Day 1;

Study Day = Event Start Date – Baseline Date, for dates before Day 1.

Study Visit

Study Visit is the nominal visit as recorded on the CRF.

Change from Baseline

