Change from baseline for a given endpoint is defined as the Study Visit value minus the Baseline Value.

Last Dose of Plecanatide

Last Dose of Plecanatide is defined as the last date that the subject received Plecanatide as determined by last date of dosing as recorded on the Study Drug Administration CRF.

Duration of Plecanatide

Duration of Plecanatide is defined as the number of days from Day 1 to the date of Last Dose of Plecanatide.

Duration on Study

Duration on study is defined as the number of days from the date of screening to the date of last follow-up visit.

Dosing Compliance

Dosing compliance will be defined by the dosing compliance ratio: the number of doses actually taken by the subject divided by the number of doses that were expected to be taken during the same period multiplied by 100.

Treatment Compliance

Treatment compliance is defined as taking equal to or greater than 80% of the drug dosage prescribed. Otherwise, the subject will be considered noncompliant with study treatment.

Rescue Medication

Dulcolax® will be provided as a rescue laxative that can be used if a subject has not had a bowel movement for at least 72 hours. Subjects will be advised that it is preferred that they do NOT take rescue medication for the period from 24 hours before to 72 hours after Day 1 of dosing.

Adverse Event

An adverse event (AE) is any untoward medical occurrence associated with the use of a drug in humans, whether or not considered to be drug related. An AE can therefore be any unfavorable and unintended sign (including abnormal laboratory finding), symptom, or disease temporally associated with the use of an investigational product or study procedure whether or not considered related to the product or procedure.

Specific gastrointestinal symptoms related to IBS-C recorded daily in the electronic Diary will be summarized separately and generally not also recorded as Adverse events.

Treatment-emergent Adverse Event

A treatment emergent adverse event (TEAE) is defined as an AE that begins or worsens in frequency and/or severity after at least one dose of study drug has been administered. Additionally, it is assumed that an Adverse Event which was reported to have started on Day 1 without an associated onset time occurred after the initiation of study drug is treatment-emergent.

Treatment-emergent Laboratory Toxicities

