5.2.4.2. Change from Baseline in Frequency of BMs and CSBMs, by Study Week

The weekly BM (and CSBM) rate for each subject will be computed, as described in [Section 3.3.7](#), for each week of the 4-week treatment period and for the two weeks of the follow-up period. A summary, by treatment group, of the mean weekly BM (and CSBM) rate and change from baseline in mean weekly BM (and CSBM) rate, for each of the 6 study weeks will be presented. The change from baseline in mean weekly BM (and CSBM) rate will be analyzed using a linear mixed-effects ANCOVA model with fixed effects for gender (stratification variable), treatment, week, the interaction of treatment and week, and the corresponding baseline value; a random intercept for subject will also be specified. The least squares (LS) mean change from baseline will be presented, by treatment groups, and the difference in LS means for each treatment group versus placebo and combined active doses within each age group versus placebo in a separate model for each age group, and overall active doses versus placebo in a separate model with 95% confidence intervals and corresponding statistical p-values.

The baseline BM (and CSBM) rate will be calculated as the average BM (and CSBM) rate for each of the two weeks preceding initiation of study drug.

The above analysis will be repeated for the PP Population.

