7. CHANGES IN THE PLANNED ANALYSES

In accordance with the FDA guidance (FDA Guidance on Conduct of Clinical Trials of Medical Products during COVID-19 Pandemic, March 2020), processes were put in place to ensure that any impacted study assessments can be identified in the study database. Any impacted assessments for subjects participating in this study will be identified in the relevant individual subject listings. Any subject discontinued due to COVID-19 disruption, will be noted as such in the subject disposition summary and associated individual subject listing.

SAP Version 2.0 changes: For the Per Protocol population, the compliance threshold for eDiary was updated to eDiary compliance of at least 70% instead of at least 80%. Overall, this eDiary compliance threshold is considered adequate in this pediatric subject population and in the context of the COVID-19 pandemic.

The Per Protocol population was also updated to expand visit windowing for Visit 3/Week 4 from the protocol-specified window of 28 +3 days. to 28 days plus or minus 3 days. Protocol-specified visit window is 28 to 31 days, however it is expected that a subject with Week 4 completed in the 25 to 31 day window, with adequate treatment compliance and diary compliance as specified for the PP Population, is reflective of 4 weeks of study treatment, as intended by the study objectives.

Clarification was added for the pharmacokinetic analyses, utilizing actual sampling times for PK parameter estimation, and also to state the definitions for Cmax, Tmax, and Cmin.

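### SAP diary Week 5 starts on Day 29 for everyone, so for subjects dosed past Day 28 up to 3 of its 7 follow-up days can be on drug

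*Combined protocol and SAP*

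**What the plan says.** - **Diary weeks.** SAP 3.3.6 lists "Week 4 (Day 22-28); Week 5 (Day 29-35"), followed by Week 6 as Days 36 to 49. SAP 3.3.7 gives the anchor: "Study Day is defined relative to Baseline (Day 1"). Protocol 8.4.2 sets Weeks 1 to 4 on the same days and defines no later week.
- **Follow-up.** SAP 1.1 states: "For 2 weeks after the last dose of study drug, subjects will continue to complete their daily electronic diaries". Protocol section 1 describes follow-up in the same way.
- **End of treatment.** Protocol 5.2.6 places Visit 3 on Day 28 with a window of +3 days, and unused drug is collected there. Protocol 6.4.1 supplies Group A with "28 days plus 4 additional tablets to allow for a +3-day window"; Group B receives 8 extra tablets on the same ground. Protocol 6.2 speaks of four consecutive weeks of dosing and protocol 9.8 of 28 days of treatment.
- **Use of the follow-up weeks.** SAP 5.2.4.2 computes BM and CSBM rates "for each week of the 4-week treatment period and for the two weeks of the follow-up period". SAP 5.2.4.1, 5.2.4.6, 5.2.4.7 and 5.2.4.8 do the same for the frequencies of abdominal pain and discomfort, fecal incontinence, defecation pain and large diameter stools.
- **Last dose.** SAP 3.3.7 has a definition: "Last Dose of Plecanatide is defined as the last date that the subject received Plecanatide", taken from the Study Drug Administration CRF. The diary-week rule does not use it.

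**The concern.** The design counts follow-up from the last dose, but the analysis counts it from Day 1. The two agree only when the last dose falls on Day 28. After a later last dose, the first days of Week 5 are treatment days reported as post-treatment days, and no rule moves or removes them.

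The SAP is also not consistent with itself. It dates post-treatment medications from the last dose. A medicine started on Day 30 by a subject still dosing is therefore not post-treatment, while that day's diary entry counts as follow-up.

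Weeks 5 and 6 are the planned off-drug data. On-drug days inside Week 5 could make an effect seem to persist after stopping, or could mask a return of symptoms.

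**Working it through.** **Inputs.** Week 5 = Days 29 to 35, which is 7 days (SAP 3.3.6). Visit 3 = Day 28 + 3 (protocol 5.2.6). Visit 4 = Day 42 + 3 (protocol 5.2.7). Kit = 28 + 4 tablets for Group A and 56 + 8 for Group B (protocol 6.4.1). Missing diary days count as 0 in the frequency endpoints (SAP 3.3.4).

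**Step 1: the plan's own figures.** The Visit 3 window is Day 28 to 28 + 3 = Day 31, as SAP section 7 also states. The supply is 28 + 4 = 32 daily doses in Group A and (56 + 8)/2 = 32 in Group B, enough to dose on each day to Day 31. A last dose on Day 28 gives two follow-up weeks on Days 29 to 42, ending at the nominal Visit 4. The SAP's Day 29 start therefore fits the nominal schedule exactly.

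**Step 2: are Weeks 5 and 6 the follow-up weeks?** SAP 3.3.6 does not label them; its sentence speaks of four treatment weeks and then lists six. The secondary sections report six study weeks, made up of four treatment weeks and two follow-up weeks. Weeks 5 and 6 must be the latter.

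**Step 3: overlap by day of last dose, L (28 to 31).** On-drug days in Week 5 = L − 28, and the share is (L − 28)/7. The two weeks after the last dose are Days L + 1 to L + 14.

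| L | On-drug days in Week 5 | Share of Week 5 | Two weeks after last dose | Days lost if Visit 4 is on Day 42 |
|---|---|---|---|---|
| 28 | 0 | 0% | Days 29–42 | 0 |
| 29 | 1 | 14% | Days 30–43 | 1 |
| 30 | 2 | 29% | Days 31–44 | 2 |
| 31 | 3 | 43% | Days 32–45 | 3 |

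Day 45 is the last day of the Visit 4 window, so a full 14 days after a Day 31 dose fits the schedule when Visit 4 is held then.

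**Step 4: illustration of size.** Assume an on-drug difference of 1.5 per week that ends at once when drug stops. The 1.5 is the SBM planning value in SAP 3.1, borrowed only for scale. The Week 5 difference that comes purely from on-drug days is 1.5 × (L − 28)/7:

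- nobody doses past Day 28: 0;
- everybody doses to Day 31: 1.5 × 3/7 = 0.64 per week;
- last doses spread evenly over Days 28 to 31: mean overlap (0 + 1 + 2 + 3)/4 = 1.5 days, or 1.5/7 = 21% of Week 5, and 1.5 × 1.5/7 = 0.32 per week.

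The documents give no distribution of last-dose days, so the supportable statement is the range 0 to 0.64. The even spread is one assumed point within it.

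**Step 5: what re-anchoring alone would do.** With L = 31 and Visit 4 on Day 42, Follow-up Week 2 is Days 39 to 45, and Days 43 to 45 have no diary. Under SAP 3.3.4 those 3 of 7 days (43%) would become zeros. With L = 25, counting from the last dose would make Follow-up Week 1 Days 26 to 32, and Days 26 to 28 would then sit in both Week 4 and follow-up. A sound fix has to deal with both cases.

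**The case against.** **Dosing past Day 28 is inferred.** Protocol 6.2 and 9.8 describe 28 days of treatment, and no section tells subjects to keep dosing until a late Visit 3. If all stop on Day 28, the overlap is zero. This limits the size, but the point stands: spare tablets are issued expressly for the window, and drug is collected only at the visit. The documents do not say what a subject seen on Day 31 does on Days 29 to 31, and those sections need to be reconciled.

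**Little depends on Week 5.** The primary analysis (SAP 5.2.2) uses the four treatment weeks. The objectives concern 4 weeks of treatment, no hypothesis about persistence or rebound is planned, and SAP 3.3.3 calls the trial exploratory. The six weeks are clearly summarised, but the text does not say whether the mixed models include Weeks 5 and 6. SBM, the source of the 1.5, is not among the SAP's follow-up endpoints. All of this stands, and it keeps the point to the secondary by-week follow-up results.

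**A reader might infer that Week 4 is wrong too**, because a subject finishing on Day 25 has 3 of 7 Week 4 days off drug. The documents do not support calling this an error. Protocol 8.4.2 and SAP 3.3.6 fix Weeks 1 to 4 identically, and analysing Days 1 to 28 regardless of dosing is a common and defensible choice. Nor does the SAP anticipate early visits. Where section 7 says "it is expected that a subject with Week 4 completed in the 25 to 31 day window", the expectation is that such a subject, if compliant, still represents four weeks of treatment. The same section restates the protocol window as 28 to 31 days and widens it only for membership of the PP Population.

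**Conclusion.** The point holds for Week 5 only. A fixed Day 29 start conflicts with follow-up defined from the last dose, and it mislabels up to 3 of 7 days (43%) for a subject whose last dose is on Day 31. This assumes that some subjects seen after Day 28 continue dosing until the visit, as the supply allows. How many do so is unknown, so the average contamination lies between 0% and 43%. The results at risk are the Week 5 summaries, and any models that include that week, for BM, CSBM, abdominal pain and discomfort frequency, fecal incontinence, defecation pain frequency and large diameter stools.

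The primary analysis is not affected, and neither are the pain severity and stool consistency analyses, which cover the treatment weeks only. The correction is modest, but the date it needs is already collected. The 14-day length of Week 6 is a separate matter: shortening it would not repair Week 5.

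**What to change.** Replace the Week 5 and Week 6 text in SAP 3.3.6 with a rule on these lines:

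1. Weeks 1 to 4 remain Days 1 to 28, regardless of dosing.
2. If the last dose of assigned study drug, active or placebo, is after Day 28, Follow-up Week 1 is days 1 to 7 after that dose and Follow-up Week 2 is days 8 to 14. On-drug days after Day 28 belong to neither period.
3. If the last dose is on or before Day 28, follow-up starts on Day 29, so that no day is counted twice.
4. When Visit 4 cuts a follow-up week short, multiply the count by 7 and divide by the days of that week up to Visit 4, instead of setting later days to 0. After a Day 31 dose with Visit 4 on Day 42, Follow-up Week 2 has Days 39 to 42, so the factor is 7/4.

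The last-dose definition in SAP 3.3.7 names plecanatide, so it should be reworded to cover placebo subjects. At most, also flag subjects whose last dose was before Day 28; no change to Week 4 is needed.

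Cost: one SAP paragraph and minor programming, using a date already on the CRF. Some subjects dosed past Day 28 will contribute up to 3 fewer follow-up days, and their scaled second week will be less precise.

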Criteria for Evaluation of Efficacy and Safety	
Primary Efficacy endpoint: Change from baseline in weekly SBM frequency over the 4 Week Treatment Period compared to placebo and across treatment groups.
 
Secondary efficacy endpoints:
 
 ○ Change from baseline in frequency and severity of abdominal pain and abdominal discomfort ○ Change from baseline in frequency of BMs, SBMs, and CSBMs ○ Time to First BM ○ Change from baseline in stool consistency (BSFS or mBSFS-C) ○ Use of Rescue Medication ○ Change from baseline in frequency of fecal incontinence ○ Change from baseline in frequency and severity of defecation pain ○ Change from baseline in frequency of large diameter stools 
Pharmacokinetic endpoints:
 
Single dose and steady state of plasma plecanatide and its major metabolite SP-338 (population modeling):
 
 ○ Plasma concentration of plecanatide/SP-338 (Note: measurable plecanatide/SP-338 levels have not been observed in the adult population) ○ PK parameters, including Cmax, Tmax, and Cmin (only if a sufficient number of plecanatide/SP-338 levels can be measured to allow computation of these parameters) 
Safety endpoints:
 
 ○ Frequency of treatment-emergent adverse events (TEAEs) ○ Withdrawals due to adverse events and serious adverse events ○ Significant shifts from Baseline values in laboratory analytes and vital signs

Statistical Methods	Sample Size and Power Considerations

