
squares mean with 95% confidence intervals will be presented for the difference between each plecanatide group and placebo.

Pharmacokinetic Analyses

Plasma plecanatide (and its major metabolite SP-338) concentrations will be assessed for all patient's pre-dose on Day 1 and at the Week 4 visit. Intensive PK sampling (30, 60, 90, and 120 minutes post dose on Day 1) will be done in a subset of approximately 70 patients at selected sites. Descriptive PK parameters will be presented and to the extent possible will be analyzed.

Safety Analyses

[figure not shown]
The Medical Dictionary for Regulatory Activities (Version 14.1 or higher) will be used to classify all AEs with respect to system organ class and preferred term. Adverse events, changes in clinical laboratory parameters, and vital signs will be analyzed descriptively. Shifts in key laboratory parameters will be summarized from Baseline to the end of the study. Similarly, shifts in toxicity of key laboratory parameters and the proportion of patients with abnormal clinical and vital sign results will be summarized.

LIST OF STUDY PERSONNEL

[figure not shown]
Sponsor:

Medical Monitor:

SAE Reporting:

Central Laboratory:

Pharmacokinetic Laboratory

Drug Manufacturer:

**Drug Packaging and
Distribution:**

TABLE OF CONTENTS

1. OVERALL DESIGN AND PLAN OF THE STUDY	17
2. INTRODUCTION	18
2.1 BACKGROUND AND RATIONALE	18
2.1.1 Irritable Bowel Syndrome with Constipation (IBS-C in Adults)	18
2.1.2 IBS-C in Children and Adolescents	18
2.1.3 Plecanatide Mechanism of Action and Pharmacology	19
2.1.4 Clinical Experience in Adults	19
2.1.5 Clinical Experience in Adults with CIC and IBS-C	19
2.2 OBJECTIVES	20
2.2.1 Primary Objective	20
2.2.2 Secondary Objective	20
2.2.3 Rationale for Dose Selection	20
2.3 RISK-BENEFIT ASSESSMENT	20
2.4 CRITERIA FOR EVALUATION OF THE STUDY	21
2.4.1 Efficacy Endpoints	21
2.4.1.1 Primary Efficacy Endpoint.....	21
2.4.1.2 Secondary Efficacy Endpoints	21
2.4.1.3 Patient Reported Outcomes.....	21
2.4.2 Pharmacokinetic Endpoints	21
2.4.3 Safety Endpoints	21
2.5 JUSTIFICATION OF THE STUDY DESIGN.....	22
2.6 PLANNED SAMPLE SIZE AND NUMBER OF STUDY CENTERS	22
3. STUDY POPULATION.....	23
3.1 INCLUSION CRITERIA	23
3.2 EXCLUSION CRITERIA	23
3.3 PREVIOUS AND CONCOMITANT MEDICATIONS	25
3.3.1 Permitted Concomitant Medications	25
3.3.2 Prohibited Prior and Concomitant Medications and Supplements	25

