8.10 SAFETY ANALYSES

Evaluation of the safety of once daily plecanatide over 4 weeks of dosing will be based on the occurrence of TEAEs, vital signs, and clinical laboratory assessments as compared with those noted in the placebo group.

The safety analyses will use the Safety Population defined in **Section 8.3**.

The frequency of SAEs, AEs leading to withdrawal from study participation, and TEAEs will be included in the primary safety tables.

Adverse events will be coded using the Medical Dictionary for Regulatory Activities (MedDRA) classifications with reference to system organ classes (SOCs) and preferred terms. Only TEAEs will be included in summary tables. Summaries of TEAEs will be presented by SOC and preferred term, by treatment. Summaries will include the frequency of TEAEs, SAEs, and AEs leading to withdrawal from study participation, by dose as well as by intensity and relationship to study drug.

Out of range laboratory tests and vital signs of potential clinical importance will also be summarized; a listing of patients with at least one out of range value will be presented by visit for that test.

Laboratory tests (hematology, serum chemistry, and urinalysis), and vital signs will be summarized as changes from baseline. Laboratory shift tables will also be produced, where applicable. Listings of laboratory tests and vital signs will also be provided.

Physical examination and medical history listings will be provided but not summarized.

Concomitant medications will be auto-encoded using the WHODD coding system with reference to Anatomical Therapeutic Classification (ATC) text and preferred terms. Summaries of concomitant medication will be presented by ATC text and preferred terms. Prior, concomitant, prior and concomitant, and post-treatment medications will be presented separately.

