5.3.2. Clinical Laboratory Assessments

Laboratory tests (hematology, serum chemistry, and urinalysis) will be summarized as changes from baseline. Laboratory shift tables from baseline to end of study will also be produced. Listings of laboratory tests will also be provided.

Toxicities for clinical laboratory will be characterized according to Common Terminology Criteria for Adverse Events (CTCAE), Version 4.03. Out of range laboratory tests will also be summarized, and a listing of subjects with at least one out of range value will be presented by visit for that test.

Moreover, “Medically Important Events” recently defined by FDA will be reported as SAEs. These include cases where:

- Aminotransferases (ALT or AST) are > 3 times the upper limit of normal (ULN) with an associated elevation of total bilirubin > 2 times ULN without evidence of hemolysis or with alkaline phosphatase < 2 times ULN or not available, or
- ALT or AST activity that is > 5 times ULN

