5.3.3. Vital Signs, Height, and Weight

Vital signs will be summarized as changes from baseline. Listings of vital signs will also be provided. A separate listing of subjects with at least one out of range value will be presented by visit for that assessment. The normal range of vital signs is summarized below:

Variable	Units	Normal Range
Systolic blood pressure	mmHg	≤ 120
Diastolic blood pressure	mmHg	≤ 80
Heart Rate	beats/minute	60 to 100
Respiratory Rate	breaths/min	12 to 25
Temperature	°C	< 38

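### SAP 5.3.3 omits the promised summary of out-of-range vital signs, and its blood-pressure ranges cannot flag a low value

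*Combined protocol and SAP*

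**What the plan says.** **Protocol.** The synopsis names as a safety endpoint "Significant shifts from Baseline values in laboratory analytes and vital signs". Its safety analysis paragraph adds that "the proportion of patients with abnormal clinical and vital sign results will be summarized". Protocol 8.10 says "Out of range laboratory tests and vital signs of potential clinical importance will also be summarized", and the same sentence also promises a by-visit listing of patients with out-of-range values. Protocol 2.4.3 is milder: clinically important changes in vital signs are to be presented.

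**SAP, laboratory tests.** Section 5.3.2 keeps both outputs. It says "Out of range laboratory tests will also be summarized" and adds a listing.

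**SAP, vital signs.** Section 5.3.3 plans changes from baseline and listings. On abnormal values it says only: "A separate listing of subjects with at least one out of range value will be presented by visit for that assessment". It then states "The normal range of vital signs is summarized below" and gives systolic pressure at most 120 mmHg, diastolic at most 80 mmHg, heart rate 60 to 100, respiratory rate 12 to 25, and temperature below 38 °C. One set of ranges serves all ages from 6 to under 18.

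**SAP, which value enters a by-visit table.** Section 3.3.6 analyses by nominal visit. An unscheduled value is used if "the unscheduled visit falls in a visit window and the scheduled visit from the same visit window has a missing value". If several values fall in one window, "the result closest to the scheduled visit date will be used for summary presentations". All assessments go into the listings.

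**The concern.** Protocol 6.3.1 says that children may be at increased risk of diarrhea and dehydration on this drug. A reader of the safety results will want to know how many patients in each dose group, compared with placebo, had an abnormal vital sign after dosing, and in particular a low blood pressure. As planned, no table gives that number, and the blood-pressure screen runs only in the direction less relevant to the named risk.

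The timing also matters. If lower limits are chosen after the treatment code is broken, any count of low pressures is post hoc.

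**Working it through.** No sample-size or power figure is involved. The check sets the sections side by side and applies the SAP's own rules.

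**Step 1: what was promised and what is planned.**

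| Output on abnormal values | Laboratory tests | Vital signs |
|---|---|---|
| Summary in protocol 8.10 | yes | yes |
| Listing in protocol 8.10 | yes | yes |
| Summary in SAP text | yes (5.3.2) | no (5.3.3) |
| Listing in SAP text | yes (5.3.2) | yes (5.3.3) |
| Toxicity or shift tables in SAP 9.1 | 6 | 0 |

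The six are three panels (chemistry, hematology, urinalysis) times two tables each (treatment-emergent toxicities, toxicity shifts): 3 × 2 = 6. Vital signs have one table, 14.3.5.1.X, a summary by visit, and an out-of-range listing, 16.2.8.7.2. SAP 7 covers COVID-19 handling, the Per Protocol rules and pharmacokinetics. It does not mention this omission.

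**Step 2: what the ranges can flag.** A pressure is flagged if systolic > 120 or diastolic > 80.

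- Illustrative 122/82 mmHg: 122 > 120 and 82 > 80, so both are flagged.
- Illustrative 65/35 mmHg: 65 ≤ 120 and 35 ≤ 80, so neither is flagged.

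Pressures with a lower limit: 0 of 2. Heart rate and respiratory rate have both limits. The two readings are test values of mine, not trial data.

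**Step 3: whether the by-visit table supplies the count.** SAP 5 defines descriptive statistics for continuous data as n, mean, median, SD, minimum and maximum. The minimum shows one patient's lowest value at a visit, not how many patients were low. Unscheduled checks normally drop out as well. A Day 5 unscheduled reading falls in the Week 1 window (Days 1 to 14). If the scheduled Day 1 value is present, that value is used, and the closest-date rule also favors Day 1. The Day 5 reading enters only if the Day 1 value is missing.

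**Step 4: what the Week 1 slot holds.** The only scheduled visit in Days 1 to 14 is Visit 2, and protocol 5.2.2 places its vital signs and safety labs before the first dose. The contacts between Visits 2 and 3 are by telephone. The Week 1 value is therefore normally drug-free. SAP 3.3.7 takes the safety baseline as the last value before randomization, and protocol 5.2.2 lists randomization ahead of these assessments. If sites follow that order, a pre-dose Day 1 laboratory value counts as post-baseline. Under the SAP 3.3.7 definition of treatment-emergent laboratory toxicity, it could then be counted as treatment-emergent.

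**The case against.** Several points on the other side are fair.

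- **Authority.** Protocol 8 lets the SAP supersede the protocol on everything but the primary analysis, and protocol 8.4 says deviations will be reported in the study report. Silence in SAP 7 is therefore not a breach in itself. This stands, but later disclosure does not supply the missing count.
- **Wording.** A reader might infer that the SAP swapped a promised by-group summary for a listing. The documents do not support that. Protocol 8.10 already promised the listing, and neither promise says by group. Presentation by group is a reasonable inference from the comparison with placebo in 8.10 and the percentage rule in 8.4.
- **Other capture.** Adverse-event tables report diarrhea and dehydration. Visit 3 chemistry includes creatinine, urea nitrogen and electrolytes, with toxicity and shift tables. A heart rate above 100 is flagged, and every value is listed. This narrows the gap without closing it.
- **Stopping rule.** A reader might infer that the ranges weaken safety stopping. They do not. Protocol 6.3 acts on graded diarrhea and dehydration through the Medical Monitor during the trial, its grades do not use blood pressure, and SAP outputs come after database lock.
- **Comparison with labs.** Laboratory values have a CTCAE grading system, while the SAP specifies none for vital signs. Six against zero therefore shows where abnormal values are tabulated, not a deficit of six tables.
- **Week 1.** A reader might infer that the plan conceals early on-drug data. The schedule itself heads Visit 2 as Week 1, Day 1, preferring scheduled values in by-visit tables is a normal convention, and the listings show everything. This part is a labelling matter.

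**Conclusion.** The point holds, and the SAP should be changed. A summary promised in the synopsis and in protocol 8.10 is kept for laboratory tests and left out for vital signs without being declared. Separately, the listing that remains cannot identify low blood pressure at any visit.

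The size is one missing table and two missing lower limits. How many patients would have a low reading, and how many unscheduled checks will occur, cannot be estimated from the documents. No efficacy result is affected.

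The conclusion rests on the SAP 9.1 table list reflecting what will be produced. The list is headed as proposed, and table shells are not in the documents. It also rests on low pressure being the relevant direction in dehydration. The Week 1 label is minor.

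**What to change.** Before unblinding:

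1. **SAP 5.3.3, ranges.** Add lower limits for systolic and diastolic pressure, set by the sponsor for each age group.
2. **SAP 5.3.3 and 9.1, table.** Add one table giving the number and proportion of subjects per treatment group with any out-of-range vital sign after the first dose, using scheduled, unscheduled and early-withdrawal values. Show low and high pressure separately. A footnote should say that any-time counts depend on how often a patient is measured.
3. **SAP 7.** If the summary is not restored, declare and justify its removal.
4. **Optional, SAP 3.3.6.** Label the Visit 2 slot for vital signs and labs as Day 1 pre-dose, and do not treat it as post-baseline.

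The by-visit table stays as it is. The cost is SAP wording, two limits per age group and one table, all from data already collected. The main drawback is the dependence on measurement frequency, which the footnote states.
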